## **Comparison of Ozone and Steroid Injection in Patients With Greater Trochanteric Pain Syndrome**

**NCT04420572 – 01.03.2021**

63 (sixty-three) patients were included in the study. Patients who were older than 18 years, had lateral hip pain for at least 3 months, had a VAS value of at least 4, had increased pain with pressing on the trochanter major, and failed conservative treatment were included in the study. The following patients were excluded from the study: Motor and/or sensory impairment compatible with radiculopathy, connective tissue disease, pregnancy, active infection, immune system disorders, untreated fracture, hip operation, steroid injection in the last 4 months, and/or hip region physical therapy, rheumatologic disease, cancer.

Evaluations were made before treatment (T0), 1 week after treatment (T1), and 1 month after treatment (T2). For the CSI group, T1 control was performed 1 week after CSI administration, and T2 control was performed 1 month after CSI administration. For the OI group, the T1 control was performed 1 week after the 4th OI administration, and the T2 control 1 month after the 4th OI administration. Physicians performing the administration and evaluation were different, thus allowing the study to be blinded. In the study, patients' Visual Analogue Scale (VAS), The Harris Hip Score (HHS) and The Nottingham Health Profile (NHP) questionnaires were filled. Patients were randomized into 2 groups according to Random Number Generation. The first group was determined as the ozone injection (OI) group and the second group as the corticosteroid injections (CSI) group.

33 patients were included in the 1st group and 30 patients in the 2nd group. The patients in the OI group received injections on the 1st, 4th, 7th and 10th days. A gas mixture containing 10 cc of 5% O3 and 95% medical O2 at a concentration of 25 µg/ml in the first application, 20 µg/ml in the second application, and 15 µg/ml in the third and fourth applications was used. It was the same physician who prepared and administered ozone. Experience has shown that a single dose of ozone application is not sufficient, it must be applied in sessions for a strong effect. Therefore, we used 4 doses of OI instead of a single dose in our study. A single dose injection was given to the patients in the CSI group. The solution to be administered to the CSI group was obtained by mixing 1 ml of 2% lidocaine and 1 ml of betamethasone (Diprospan 2 mg/1ml+5 mg/1ml). It was the same physician who prepared and administered the solutions. In the studies, it was generally applied as a single dose and mixed with local anesthetic (LA). Therefore, in our study, we also applied it as a single dose by mixing it with LA. There will be pre-injection, postinjection 1st week and 1st month controls.

Comparison of Ozone and Steroid Injection in Patients With Greater Trochanteric Pain Syndrome

NCT04420572 – 01.08.2021

Statistical Analysis

Statistical analyses were done using SPSS version 20 statistical software (IBM Corp., Armonk, NY). Average, standard deviation and frequency were used as descriptive statistical methods. Shapiro-Wilk and Kolmogorov-Smirnov tests were used to evaluate the distribution of numerical data. Since the data were not suitable for normal distribution, Mann-Whitney U test was used to measure the difference between the groups and Willcoxon test was used to measure the temporal process. Bonferroni test was used to detect important differences. Pearson Chi Square test was used for the differences between discrete variables. The results were evaluated at a 95% confidence interval and $p < 0.05$ significance level.

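### The between-arm comparison leaves the collected T0 scores unused and names no ozone–steroid difference with a 95% confidence interval; the test is valid, so this is a cheap improvement and not an error

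*SAP*

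**What the plan says.** The SAP is a single paragraph. For numerical data it gives a reason, "Since the data were not suitable for normal distribution", and then the tests: "Mann-Whitney U test was used to measure the difference between the groups and Willcoxon test was used to measure the temporal process". It names no outcome, visit, covariate or model. Chi-square is kept for discrete variables.

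The listed summaries are within-arm: "Average, standard deviation and frequency were used as descriptive statistical methods". A confidence interval appears once, "The results were evaluated at a 95% confidence interval", alongside the significance level and tied to no quantity. It may mean no more than that level. On multiplicity the SAP says "Bonferroni test was used to detect important differences", without a family.

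The protocol shows what was available. On the schedule: "Evaluations were made before treatment (T0), 1 week after treatment (T1), and 1 month after treatment (T2". On outcomes: "Visual Analogue Scale (VAS), The Harris Hip Score (HHS) and The Nottingham Health Profile (NHP) questionnaires were filled". On numbers: "33 patients were included in the 1st group and 30 patients in the 2nd group".

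**The concern.** Each patient has a T0 score on each scale, and the comparison between arms does not use it. Where T0 predicts follow-up, an analysis that accounts for T0 is more sensitive for the same 63 patients. Non-normality does not rule this out, because rank-based adjustment exists.

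The outputs named are a p-value between arms and summaries within arms. With 33 v 30 patients, a non-significant p-value does not tell a reader whether the two injections perform alike or the trial was too imprecise to say. Only an estimate of the difference with its interval shows that.

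A smaller matter is that the SAP does not say whether Mann-Whitney is applied to follow-up scores or to changes from T0. Over-time analysis is given to Wilcoxon, so scores at each visit are the more natural reading, but this is not stated. On its own this would be only a missing detail.

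**Working it through.** **Inputs from the documents.** 33 ozone (OI) and 30 corticosteroid (CSI) patients, 33 + 30 = 63, which agrees with the stated total; three scales; T0, T1 and T2; significance level 0.05. The documents give no power, effect size or SD, so there is no planned figure to reproduce.

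**Assumptions.** Two-sided tests; a difference of 0.6 SD (0.3 SD also tried); T0-to-follow-up correlation r = 0.3, 0.5 or 0.7. The strict Bonferroni case is 3 scales × 2 visits = 6 tests, 0.05/6 = 0.0083.

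**Step 1: normal approximation.** Power = Φ(0.6/SE − 1.96). The base SE is √(1/33 + 1/30) = 0.252 SD.

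- Mann-Whitney on scores: SE = 0.252/√(3/π) = 0.258. Power = Φ(2.32 − 1.96) = 64% at every r.
- Mann-Whitney on change: multiply 0.258 by √(2(1 − r)). Power = 50, 64 and 85%.
- T0-adjusted mean difference: SE = 0.252 × √(1 − r²) = 0.241, 0.218 and 0.180. Power = 70, 78 and 92%. This is the best case under normality; a rank version gives up a little.

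**Step 2: simulation of the rank tests** (33 v 30, 8,000 trials per setting). Quade's test ranks T0 and follow-up over all patients, regresses the follow-up ranks on the T0 ranks ignoring arm, and compares the residuals between arms. Power (%) at r = 0.3/0.5/0.7:

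| Setting | Mann-Whitney, scores | Mann-Whitney, change | Quade |
|---|---|---|---|
| Normal, 0.6 SD, 0.05 | 62/63/63 | 48/63/84 | 65/73/87 |
| VAS-type*, 0.6 SD, 0.05 | 63–64/65–67/67–71 | 52–55/66–67/84 | 65/73/85–86 |
| Skewed, 0.6 SD, 0.05 | 96/96/96 | 79/89/98 | 97/98/100 |
| Skewed, 0.3 SD, 0.05 | 55/55/55 | – | 58/65/79 |
| Normal, 0.6 SD, 0.0083 | 35/35/34 | 23/35/60 | 39/47/66 |

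*Whole points 0–10, SD 2, entry at 4 or more, shift 0.6 × 2 = 1.2 points. The entry cut lowers r to about 0.22–0.25/0.38–0.43/0.57–0.62. For skewed (lognormal) data, r is the correlation before transformation.

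Type I error of all three tests is 4.5–5.2%.

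**Step 3: low correlation.** Normal, 0.6 SD, 0.05, scores v Quade: 62.2 v 61.7% at r = 0, 62.6 v 62.3% at 0.1 and 63.1 v 64.1% at 0.2. At 0.0083, Quade leads by 1.5 points even at r = 0 (35.4 v 33.9%), so part of the strict-case gain is not due to T0.

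**Step 4: two tests can disagree.** Trials (%) in which Mann-Whitney on scores and Quade give different verdicts, at r = 0.3/0.5/0.7:

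| Setting | 0.05 | 0.0083 |
|---|---|---|
| Normal, 0.6 SD | 9/17/28 | 9/19/36 |
| Skewed, 0.6 SD | 2–4 | 6/10/14 |
| Skewed, 0.3 SD | 9/18/29 | – |

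Taking whichever is significant gives about 5.6–8.4% type I error at 0.05. Score and change forms of Mann-Whitney differ in 32/32/35% of normal trials at 0.6 SD and 0.05, which is why the form needs confirming.

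**Step 5: the interval.** The Hodges-Lehmann shift is the median of the 33 × 30 = 990 OI minus CSI differences. Its expected 95% width for normal data is 2 × 1.96 × 0.258 = 1.01 SD; simulation gives 1.04 SD, with coverage of 94.2–95.8% over normal and skewed data. A null result could therefore leave differences of about half an SD either way. The interval disagrees with Mann-Whitney in under 1% of trials with continuous data. With whole-point VAS at 0.6 SD the figure is 36–42%, always because a limit falls exactly on 0. The Brunner-Munzel interval disagrees in at most 2% in every setting (coverage 93.2–95.4%).

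**The case against.** The strongest case is that nothing here is broken. Mann-Whitney is valid under randomisation, no part of the documents promises adjustment, and the one ambiguity can be settled in a line. All of this stands, and it is why the point is an improvement only.

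Second, the power gain does not reach the decision. The SAP is written in the past tense, so a T0-adjusted test added now is post hoc. If Mann-Whitney continues to govern, the trial's power is unchanged. This also stands. The gain also depends on a correlation that the documents do not give, and the VAS entry threshold narrows the T0 range and pulls the correlation down.

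Third, a reader could build a difference from the arm means and SDs. That is possible, but it describes means, which Mann-Whitney does not test, in data that the SAP calls non-normal.

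Fourth, visits are timed from the fourth injection (day 10) in the OI group and from the only injection in the CSI group. T1 and T2 thus fall about 10 − 1 = 9 days later after first treatment in the OI group. An interval would inherit this offset and should be read with it. It is a separate matter and no reason to omit the interval.

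Stronger readings are tempting but unsupported. A reader might infer an inflated false-positive rate. Running both score and change forms and keeping the better one would give 7.8–9.7% at 0.05, but nothing in the documents suggests that this was done. A reader might also infer that adjustment always gains power; Step 3 shows that it does not.

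**Conclusion.** The point holds as a modest, worthwhile improvement. The SAP's one between-arm test for numerical outcomes ignores T0 and comes with no estimate or interval for the ozone–steroid difference. That the test covers VAS, HHS and NHP is inferred, since the SAP names no outcome.

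The missing estimate is the firmer part, because it depends on no assumed correlation. The value of adjustment is conditional. For normal data at 0.6 SD and 0.05 it is about 3 points of power at r = 0.3, 10 at 0.5 and 24 at 0.7, and nothing material up to 0.2. With strong skew at 0.6 SD, both tests are already near the ceiling. These figures describe a supporting analysis and do not show that the documented conclusion is underpowered or wrong.

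**What to change.** 1. Keep Mann-Whitney as the governing test and have the sponsor confirm that it compares T1 and T2 scores between arms.
2. For each scale and visit, report the OI minus CSI Hodges-Lehmann shift with its 95% confidence interval. For any scale recorded in whole points, also report the Mann-Whitney probability (the chance that an OI score exceeds a CSI score, ties counted half) with a Brunner-Munzel 95% interval.
3. Add Quade's rank ANCOVA on the same scale's T0 score as a sensitivity analysis. Label it as added after the SAP dated 01.08.2021, apply the same Bonferroni handling with the family stated, and report it whatever it shows.
4. Base the ozone–steroid conclusion on the between-arm results and not on the within-arm Wilcoxon tests.

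The cost is a few analyses on data already held. The risk is conflicting verdicts at the rates in Step 4, so the added test must not replace the documented one.

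### The only named test of change from T0 cannot compare the arms, and no between-arm analysis adjusts for T0; a baseline-adjusted contrast should carry the conclusion

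*SAP*

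**What the plan says.** The SAP (Statistical Analysis) divides the work in one sentence. For the comparison of arms, "Mann-Whitney U test was used to measure the difference between the groups". For change over time, "Willcoxon test was used to measure the temporal process". It then adds that "Bonferroni test was used to detect important differences", without giving the family of tests or the adjusted level.

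The SAP does not say:
- whether Mann-Whitney is applied to T1 and T2 scores, to change from T0, or to both;
- whether the Wilcoxon test is run in each arm or on pooled patients (in each arm is the natural reading);
- which test carries the conclusion about treatment.

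It names no group-by-time analysis and no analysis adjusted for T0.

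From the Protocol: "Patients were randomized into 2 groups according to Random Number Generation" and "33 patients were included in the 1st group and 30 patients in the 2nd group". Both arms receive an active injection. A patient qualified only if he or she "had a VAS value of at least 4", and VAS is also an outcome, alongside the Harris Hip Score and the Nottingham Health Profile. Assessments are at T0, T1 (1 week) and T2 (1 month). No outcome or time point is named as primary.

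**The concern.** The trial asks whether ozone and steroid differ. A paired test inside one arm asks whether scores moved in that arm. With no untreated arm, movement can come from the injection, the natural course of the condition, expectation or, for VAS, regression to the mean caused by the entry threshold. The p-value cannot tell these apart. Bonferroni moves the significance threshold but does not change what the test measures.

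Two misreadings are then open. One is to report that an arm worked because its Wilcoxon p-value is small. The other is to report that one treatment is better because its arm reached significance and the other did not. Nothing in the plan ranks the between-arm test above the Wilcoxon results, so nothing blocks either reading.

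There is also a matter of precision. T0 is measured in both arms, yet no named between-arm analysis adjusts for it.

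**Working it through.** The documents give no SD, correlation, target difference or power, so there is no planned figure to reproduce. From the Protocol come the arm sizes (33 ozone, 30 steroid) and the entry threshold (VAS of at least 4). From the SAP comes the 0.05 level, taken as two-sided. Everything else below is assumed.

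**1. How often identical arms disagree.** Change scores are normal with the same mean change d (in SDs of change) in both arms, with 10,000 simulated trials per d. A Wilcoxon signed-rank test is run in each arm and a Mann-Whitney test on change between arms. With arm-wise rejection rates p1 and p2, the chance that exactly one arm is significant is p1(1 − p2) + p2(1 − p1).

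| d | p1 (n = 33) | p2 (n = 30) | Exactly one arm significant | Mann-Whitney on change |
|---|---|---|---|---|
| 0 | 4.6% | 5.3% | 9.5% | 5.0% |
| 0.2 | 18.8% | 18.1% | 29.9% | 4.8% |
| 0.3 | 37.5% | 34.3% | 46.1% | 5.0% |
| 0.4 | 58.2% | 54.9% | 49.7% | 5.2% |
| 0.5 | 77.8% | 74.1% | 36.6% | 4.6% |
| 0.8 | 99.0% | 98.5% | 2.5% | 4.7% |

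Check by formula at d = 0.3: 0.375 × 0.657 + 0.343 × 0.625 = 0.246 + 0.214 = 0.461.

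**2. Regression to the mean alone.** VAS is normal with SD 2, patients are selected at T0 ≥ 4, and there is no true change in either arm. The population mean is varied over 4, 5 and 6 and the test-retest correlation over 0.5, 0.7 and 0.9, with 1,000 trials per setting.

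- Mean VAS change: −0.81 to −0.06.
- Wilcoxon significant in a given arm: 7% to 66%. The highest rates come from population mean 4 with correlation 0.5; with population mean 6 the range is 7% to 13%.
- Mann-Whitney between arms: 3.4% to 5.9% on follow-up scores and 3.7% to 5.7% on change.

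The between-arm test holds its level on either quantity, because randomisation makes the shared regression cancel.

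**3. What adjustment for T0 buys.** Normal approximation, 80% power, unadjusted comparison of follow-up means:

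(1.960 + 0.842) × √(1/33 + 1/30) = 2.802 × 0.2523 = 0.71 SD.

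Let r be the correlation of T0 with follow-up among enrolled patients, with equal SDs at both times. ANCOVA multiplies this by √(1 − r²), and analysing change multiplies it by √(2(1 − r)). Both are expressed in SDs of the follow-up score:

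| Assumed r | Follow-up score | Change from T0 | ANCOVA |
|---|---|---|---|
| 0.3 | 0.71 | 0.71 × 1.18 = 0.84 | 0.71 × 0.95 = 0.67 |
| 0.5 | 0.71 | 0.71 × 1.00 = 0.71 | 0.71 × 0.87 = 0.61 |
| 0.7 | 0.71 | 0.71 × 0.77 = 0.55 | 0.71 × 0.71 = 0.50 |

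ANCOVA detects the smallest difference in each row, whichever quantity Mann-Whitney was meant for. A simulation with an assumed true VAS difference of 1.2 points points the same way: power was 71% to 87% for rank ANCOVA against 64% to 73% for Mann-Whitney on follow-up scores, across assumed inputs.

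**The case against.** The strongest reply is that the plan already names a between-arm test, in the same sentence as the Wilcoxon. Under randomisation that test is valid on follow-up scores or on change, and step 2 confirms that it holds its level. No text says that a within-arm p-value, or a one-arm-only result, will be read as a treatment effect. The disagreement rates in step 1 are therefore not the error rate of any decision rule in the SAP. All of this stands.

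A reader might infer more: that the plan judges ozone against steroid by within-arm p-values, or that Mann-Whitney is confined to raw scores and the plan is therefore wrong. The documents support neither. The SAP is silent on what Mann-Whitney is applied to, and it gives the Wilcoxon only the description of change over time.

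The size also depends on assumptions. With a population mean well above the threshold, regression to the mean adds little, and no baseline VAS is given. Only VAS has an entry threshold, so the argument does not carry over directly to the Harris Hip Score or the Nottingham Health Profile. Natural course and expectation still apply to all three.

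What the reply does not remove is the silence on which test decides, and the lack of any between-arm analysis adjusted for T0.

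**Conclusion.** The point holds as a cheap improvement, not as an error in the plan. The Mann-Whitney comparison is valid. The gaps are that its target quantity is unstated, that no between-arm analysis adjusts for T0, and that the only test named for change from T0 cannot compare the arms and is not labelled descriptive.

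At these arm sizes the risk of misreading is material if the common change is moderate: identical arms disagree in about 46% to 50% of trials at 0.3 to 0.4 SD. It falls to 2.5% at 0.8 SD, where both arms are nearly always significant. Those figures assume normal change scores with equal spread. The gain from adjustment is a detectable difference of about 0.61 SD in place of 0.71 SD if r is 0.5, with a range of 0.67 to 0.50 SD for r from 0.3 to 0.7.

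**What to change.** Replace the sentence on the group and time tests with wording such as: 'T1 and T2 scores are compared between the two arms adjusting for the T0 score (ANCOVA, or rank ANCOVA), with the estimated difference and its 95% CI. This between-arm contrast carries the conclusion on ozone against steroid. Wilcoxon results within each arm are descriptive only, and significance in one arm but not the other is not evidence of a difference.' If rank ANCOVA supplies the p-value, state how the estimate and its interval on the original scale are obtained.

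Cost: SAP wording and a re-run on T0, T1 and T2 data already collected. Within-arm p-values stop being headline results. Because the SAP describes completed analyses in the past tense, the new analysis must be marked as added later, with the Mann-Whitney results kept beside it.

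Limits: the change does not choose a primary outcome or time point. It also does not remove the visit-timing offset. The Protocol counts ozone visits from the fourth injection (day 10) and steroid visits from the single injection. Taking the steroid injection as day 1, ozone patients are assessed about 10 − 1 = 9 days later after first treatment, so natural course need not cancel fully between arms. That needs its own treatment.

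### Holm step-down could replace plain Bonferroni at the same family-wise error; how much power it recovers depends on a family and effects that the documents do not state

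*SAP*

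**What the plan says.** The SAP, under Statistical Analysis, compares the arms as follows: "Mann-Whitney U test was used to measure the difference between the groups". For change over time, "Willcoxon test was used to measure the temporal process". The next sentence is the whole of the multiplicity plan: "Bonferroni test was used to detect important differences". The threshold is given as "The results were evaluated at a 95% confidence interval and $p < 0.05$ significance level".

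The protocol supplies the structure. On visits: "Evaluations were made before treatment (T0), 1 week after treatment (T1), and 1 month after treatment (T2"). On outcomes: "In the study, patients' Visual Analogue Scale (VAS), The Harris Hip Score (HHS) and The Nottingham Health Profile (NHP) questionnaires were filled". On arm sizes: "33 patients were included in the 1st group and 30 patients in the 2nd group".

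Neither document says which comparisons form a family, what the divisor is, or whether the correction applies to the Wilcoxon tests, the Mann-Whitney tests or both. Neither mentions a stepwise procedure, and neither names a primary outcome or contrast.

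**The concern.** Single-step Bonferroni holds each of k comparisons to 0.05/k, however many of the others have already been rejected. Holm relaxes the threshold as rejections accumulate and gives the same family-wise guarantee.

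The difference matters most where some comparisons are easy and one is hard. The within-arm tests may be like that. Patients enter with a VAS of at least 4 and are then treated, so T0-T1 and T0-T2 may well be rejected easily. Bonferroni would still hold T1-T2 to 0.05/3 = 0.0167, whereas Holm would by then test it at 0.05. T1-T2 is the only pair that directly tests whether the effect fades or grows between 1 week and 1 month. A real change there could be missed more often than a 5% family-wise error requires.

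**Working it through.** **Inputs from the documents.** Alpha 0.05 (SAP). Three visits, three instruments, and arms of 33 and 30, which sum to 63 (protocol). There is no power or sample-size figure to reproduce.

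**Assumptions.** Two-sided tests, normal scores with SD 1, and correlation 0.5 between visits. The SD of a paired difference is then √(2 × (1 − 0.5)) = 1, so effects in SD units are also standardised paired effects d. The within-arm family is taken as T0-T1, T0-T2 and T1-T2, so k = 3.

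**Step 1: dominance, with no effect size needed.** Holm compares the ordered p-values with α/k, α/(k−1), …, α and stops at the first failure.
- Any p-value at or below α/k passes every one of these thresholds, so Holm rejects all that Bonferroni rejects.
- Suppose m hypotheses are true. When Holm first rejects a true one, at most k − m others have gone before, so its threshold is at most α/m. The chance that any of m true hypotheses has p ≤ α/m is at most m × α/m = α, under any dependence.
- Simulation (4,000 runs) agrees. With no effects, family-wise error was 4.4% for both procedures at n = 30 and 3.9% for both at n = 33. With only T1 = T2 true, Holm's error was 4.4% to 4.6%.

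**Step 2: T1-T2 when both baseline comparisons are rejected.** The normal approximation is power = Φ(d√n − z), with z = 2.394 at 0.0167 and z = 1.960 at 0.05. For n = 30 and d = 0.4, d√n = 0.4 × 5.477 = 2.191.
- Bonferroni: Φ(2.191 − 2.394) = Φ(−0.203) = 42%.
- Holm: Φ(2.191 − 1.960) = Φ(0.231) = 59%.
- The gain is about 17 points. The noncentral t gives 18.5.

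Simulated signed-rank tests:

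| T1-T2 effect (SD) | n = 30, Bonferroni → Holm | Gain, n = 30 | Gain, n = 33 |
|---|---|---|---|
| 0.2 | 8.0% → 18.7% | 10.7 | 9.6 |
| 0.3 | 19.9% → 35.2% | 15.3 | 15.7 |
| 0.4 | 35.4% → 53.8% | 18.4 | 19.5 |
| 0.5 | 56.4% → 74.1% | 17.6 | 17.4 |
| 0.6 | 73.9% → 87.5% | 13.6 | 12.0 |
| 0.8 | 95.4% → 98.7% | 3.3 | 2.1 |

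By formula the gain is about 5 points at 0.1 SD and about 0 at 1.0 SD.

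The cost can also be put in patients. For 80% power, testing at 0.0167 instead of 0.05 needs ((2.394 + 0.842)/(1.960 + 0.842))² = (3.236/2.802)² = 1.33 times as many, still provided that both baseline comparisons are rejected.

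**Step 3: a moderate baseline change (T0-T1 effect 0.5 SD).** Holm then reaches 0.05 less often.
- If improvement continues after T1, the gain is 10 to 13 points at a T1-T2 effect of 0.3 SD (n = 30: 18.5% → 28.7%; n = 33: 20.6% → 33.2%) and about 15 points at 0.5 SD.
- If the benefit fades after T1, T0-T2 is seldom rejected, and the gain is about 4 to 6 points at 0.3 to 0.5 SD.

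**Step 4: other families.** The largest possible gap between testing at α/k and at α is 11 points for k = 2, 17 for k = 3 and 27 for k = 6 (normal approximation).

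For the arm comparison, take three outcomes × two post-treatment visits = 6 Mann-Whitney tests, 33 v 30, correlation 0.5. Mean power per true effect:

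| True effects | Bonferroni | Holm |
|---|---|---|
| 1 of 6, at 0.7 SD | 48.3% | 48.3% |
| 2 of 6, at 0.7 SD | 49.0% | 50.4% |
| 3 of 6, at 0.7 SD | 49.3% | 52.2% |
| 6 of 6, at 0.7 SD | 48% | 59% |
| 6 of 6, at 0.4 SD | 11.8% | 14.4% |

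**The case against.** Bonferroni is valid and controls the error rate. Preferring Holm is a matter of efficiency, and that stands.

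A reader might infer that the SAP gives away a fixed 14 to 19 points of power on T1-T2. The documents do not support this. That range needs a three-pair family that includes T1-T2, near-certain rejection of both baseline comparisons, and a T1-T2 effect of 0.3 to 0.5 SD, which is close to the peak of the gain curve. None of these is written down. If the Wilcoxon tests cover only change from baseline, there is no T1-T2 test to lose power on.

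Nor do the documents single out T1-T2. The title asks about ozone against steroid, and T0-T2 already tests for benefit at 1 month. For the comparison of arms, Holm gains nothing if only one of six effects is real.

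Two further points stand. The undefined family is the more basic gap, because no power loss can be computed until it is settled. And the simulations use normal scores although the SAP reports non-normal data, so the sizes are illustrative. Dominance does not depend on the distribution, provided that the individual p-values are valid.

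**Conclusion.** The point holds as a free or cheap improvement. On the natural reading the plan uses single-step Bonferroni, and Holm is never worse at the same family-wise error. That conclusion needs no assumption about effects, correlations or which family is meant.

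Only the size of the gain is conditional. For three visit pairs with both baseline comparisons rejected, it peaks at about 17 to 20 points for T1-T2 and shrinks towards zero for very small or very large effects. It is smaller again when the change from baseline is moderate, and depends on how many effects are real when the family is the six between-arm tests. It would be wrong to read this as a defect that invalidates the analysis, or as a known power loss in this trial.

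**What to change.** Replace the Bonferroni sentence in the SAP with wording that settles the family and the procedure together:

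> Within each family (the three visit pairs for each outcome and arm; the between-group tests across outcomes and post-treatment visits), p-values are adjusted by the Holm step-down method: the smallest is compared with 0.05/k, the next with 0.05/(k−1), and so on, stopping at the first non-rejection.

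Report raw and Holm-adjusted p-values side by side.

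The SAP is written in the past tense and already reports that the data were not normal, so the data appear to have been examined. If results have been seen, label the change as post hoc.

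The cost is this sentence and a spreadsheet adjustment of p-values already produced, with no extra patients or visits. One small downside is that Holm has no simple matching simultaneous confidence intervals. The SAP refers to a 95% interval but plans no simultaneous ones, so nothing planned is lost.
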